2.6.1.2 Spectral domain optical coherence tomography (SD-OCT)

The following secondary efficacy parameters based on SD-OCT will be analyzed as given below.

2.6.1.2.1 Central sub-field retinal thickness (CSFT)

Summary statistics of central sub-field retinal thickness (CSFT) measured by SD-OCT for nAMD patients will be presented by visit along with change and percentage change from Baseline in CSFT.

The number and percentage of patient with CSFT category ($< 300, \ge 300 - 450, \ge 450 - < 650, \ge 650 \text{ (µm)}$) will be presented by visit.

The above analysis will be done only on the study eye. The analysis will be performed on FAS.

2.6.1.2.2 Presence of fluid (YES/NO)

The number and percentage of patients with below fluid will presented by visit.

- 1. Intraretinal fluid
- 2. Subretinal fluid
- 3. Sub-RPE fluid
- 4. Without IRF or SRF
- 5. Without any fluid (IRF/SRF/sub-RPE)
- 6. In case of sub-RPE / PED : nature : (serious PED / fibrovascular PED / mixed PED)

Volume (mm³) and height (µm) of intraretinal fluid, subretinal fluid and/or sub-RPE fluid will be presented the summary statistics (n, mean, std, median, min and max) by visit, if available.

The above analysis will be done only on the study eye. The analysis will be performed on the FAS.

2.6.1.2.3 Dry retina

The proportion of patients without both fluids (IRF and SRF), without IRF, without SRF, without sub-RPE will be presented by visit, separately, up to Week 48/Week 50.

The proportion of patients without fluid (IRF and SRF) and having fluid (IRF and/or SRF) in entire study will be presented.

The 95% confidence interval (CI) for proportion using the Clopper-Pearson method will be provided by visit and overall.

The above analysis will be done only on the study eye. The analysis will be performed on the FAS.

2.6.1.2.4 Time to dryness

The median time to dryness will be obtained from Kaplan-Meier (KM) analysis along with 2-sided 95% CI will be presented. KM plot will be provided. Detailed KM results will be presented including time (week), number of patients under risk at visit (without dry retina), number of patients with dry retina at visit (event), probability of dry retina (survival probability) at visit and 95% CI at visit.

Variable	Definition	
Start date	Start date of IVT injection	
Event	Dry retina (absence of IRF and/or SRF)	
End date of event	Start date of first dry retina	
Censoring (end date)	Earliest of:	
Absence of dry retina until EOS		
Early discontinuation without dry retina		
Duration of time	(End date – start date) +1	

The above analysis will be done only on the study eye. The analysis will be performed on the FAS.

2.6.1.2.5 Maximum duration of dryness

The median of maximum duration of dryness until Week 48/50 will be presented. The median will be obtained from the KM analysis along with 2-sided 95% CI. KM plot will be provided.

Detailed KM results will be presented including time (week), total number of patients having fluids (risk), number of patients under achieved maximum duration (event), probability of maximum duration of dryness (survival probability) and 95% CI.

Variable	Definition	
Start date	Start date of treatment	
Event	Dryness	
End date of event	Start date of dryness	
Censoring (end date)	Earliest of:	
	Absence of dryness until EOS	

		Early discontinuation with absence of dryness
Duration of	time	(End date – start date) +1 (Maximum duration will be used)

The above analysis will be done only on the study eye. The analysis will be performed on FAS.

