### **Treatment period: Day 1 to Week 40/Week 44**

The Screening Visit and Baseline Visit (see [Table 8-1](#)) are the same visit.

One time re-assessment of patients is allowed, except for the purpose of capturing new BCVA or imaging assessments that previously failed to qualify the patient (except if image quality is poor and needs to be redone). As long as testing can be repeated within 14 days of the first screening, the other screening assessments do not need to be repeated. If rescreening is to occur beyond 14 days from the original Screening Visit date, then all screening procedures must be repeated. Medical judgment should be exercised to ensure that treatment of nAMD is not withheld in order for a patient to participate in the study.

After confirmation of eligibility, patients will be included in the study. A study visit schedule will be established at the time of Screening/Baseline Visit for all patients. All efforts should be made to adhere to the study visit schedule within a  $\pm 7$ -day window. For a given protocol visit, assessments can be performed on 2 consecutive days, provided both days are within the  $\pm 7$ -day window. Treatment (including at Screening/Baseline) is intended to be administered on the day of the study visit, or if this is not possible, within 3 days after the study visit when the per-protocol assessments will have taken place. If study visit assessments and the corresponding treatment occur on separate days, a repeat safety check-up should be performed prior to treatment of the eye and results documented in the source documents.

The Screening/Baseline Visit is defined as Screening/Baseline/Day 1. For all patients, the last potential study treatment will be at the Week 40 visit or at the Week 44 visit depending on whether patients receive the study treatment under the q8w or under the q12w schedule. The initiation phase starts on Day 1 and ends on Week 8. The q12w/q8w treatment regimen starts on Week 16 and ends on either Week 40 or Week 44 (see [Section 6.7.2](#)).

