Date	Reason for update	Outcome for update	Section and title impacted (Current)
	Update in population for disposition and protocol deviation	Population set for disposition table and listing updated	Section 2.3.1 and 2.3.2
	Update in baseline characteristics	nAMD category added	Section 2.3.4
	Update in ocular category	Ocular category was updated	Section 2.3.5, 2.4.2, 2.4.3 and 2.9.1
	Update in treatment exposure	New category added	Section 2.4.1
	Update in unit	CNV lesion area unit updated	Section 2.5.1
	Update in BCVA group	Loss of BCVA category updated	Section 2.6.1.4
	Update in date	Start date and end date consideration updated	Section 2.6.1.5.1
		Start date consideration updated	Section 2.6.1.6.1
	Update in CPF and fundus examination question	Vasculitis added in CFP and fundus examination	Section 2.8.1 and 2.8.5
	Update in FAF question	Foveal atrophy added in FAF question	Section 2.8.2
	Update in AEs section	Added procedure related, remove EudraCT requirement	Section 2.9.1
	Update in AESI analysis	Details for AESI analysis is added	Section 2.9.1.1
	Update in sample size calculation	Sample size re-estimation	Section 3
	Added protocol change analysis	Added protocol change analysis for estimand	Section 4
	Update in statistical methodology	SAS code for correlation and Bland-Altman plot is deleted. Added code AESI derivation	Section 5.4
	Update in protocol deviation list and severity code	New protocol deviation category added, severity updated and patient classification updated	Section 5.5
05-04-2023	Amendment V3.0		

Date	Reason for update	Outcome for update	Section and title impacted (Current)
	Update in visit window	Lower limit for Week 44 updated	Section 2.1.2
	Dropped category for ≤ Week 12 and > Week 12	Under drug exposure ≤ Week 12 and > Week 12 dropped	Section 2.4.1
	Update in sequence of variable	Sequence of expected variable changed	Section 2.6.1.2.4, 2.6.1.2.5, 2.6.1.5.1
	Update in Date imputation rule	The same method for date imputation used for medical history (nAMD)	Section 5.1.3
	Updated in SAS code for t-test	SAS code for t-test updated	Section 5.4
15-06-2023	Addendum V1.0		
	Added definition for maximum duration of dry retina	Added definition for maximum duration of dry retina	Section 2.1.1 General definitions
	Updated date and censor	Logic for start date, end date and censor was updated	Section 2.6.1.2.5 Maximum duration of dryness

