2.1.1 General definitions

Study treatment: This is a single-arm study and all patients will be treated with brolucizumab 6 mg. Three loading injections (at Screening/Baseline/Day 1, Week 4 and Week 8), followed by maintenance treatment from Week 16/Week 20 up to Week 40/Week 44. The investigator can individualize treatment intervals depending on disease activity, to adjust patient's injection regimen.

Study treatment start and end date: Study treatment start date is defined as the first date study treatment is administered and recorded on the treatment administration record (DAR) electronic case report form (eCRF) page. Similarly, study treatment end date is defined as the last date of study treatment is administered and recorded on the study treatment completion CRF page.

Generally, study day 1 is considered as the day of inclusion of the patient. However in this study, treatment is intended to be administered on the same day or if this is not possible, within 3 days after the day of inclusion of the patient.

Study day will be calculated as (event date – study treatment start date + 1 day) for events that occurred on or after study treatment start date (e.g. visit, AEs). For events prior to study treatment start date (e.g. time since diagnosis), study day will be negative and calculated as (event date – study treatment start date).

Baseline and post-baseline: Baseline value refers to the value of the last non-missing measurement collected prior to administration of the first dose of study treatment (Screening or Baseline visit). Intraocular pressure (IOP) will be assessed in the study eye, pre-dose and post-dose at every injection. The last available assessment taken prior to the first IVT injection of study treatment is taken as the "Baseline" assessment.

A "post-baseline" value refers to a measurement taken after the first dose of study treatment. When assessments and treatments take place on the same day, treatment must occur after completion of the efficacy assessments and pre-injection safety measures (tonometry, slit lamp and fundus examinations). If study visit assessments and the corresponding treatment occur on separate days, a repeat safety check-up will be performed prior to treatment of the eye and

results documented in the source documents. More post-baseline safety measurements will be recorded in source document; visit window will be applied to OCT and IVT visits.

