Change from Baseline: The difference of measure between post-baseline and Baseline is called change from Baseline.

Percent change from Baseline: The percent change from Baseline will be calculated as below: ((post-baseline value – Baseline value) /Baseline value)*100.

On-treatment period: The on-treatment period lasts from the date of first administration of study treatment to 28 days after the date of the last actual administration of any study treatment.

Treatment duration: The maximum planned duration of treatment for each patient is 40 to 44 weeks in accordance with the designated treatment regimen. Discontinuation of study treatment for a patient occurs when study treatment is stopped earlier than the protocol planned duration and can be initiated by either the patient or the investigator.

Treatment discontinuation: When patients discontinue study treatment but continue in the study, the efficacy data will be used at the time the patient stopped study treatment.

Dry retina: Absence of fluid (IRF/SRF/sub-RPE) will be considered as dry retina.

Event for maintenance q12w interval: In case the investigator selects q12w interval for a patient and the patient maintains the q12w interval until the first q8w interval has started then this will be considered as an event. In case the investigator maintains q12w interval (does not select q8w interval at any time in study) until EOS or patients got early discontinuation from study then patients will be considered as censored.

Event for no disease activity: When patients will be with no disease status as per investigator decision after last dose in initiation phase then the patients will consider as event for disease activity. If patients with active disease status or early discontinue then patients will be considered as censored for disease activity.

Event for dry retina: When patients have absence of fluid then it will be considered as an event of dry retina. If patients have a presence of fluid before/at EOS or early discontinuation then will be censored.

Maximum duration of dry retina: The longest consecutive interval of dryness will be considered as maximum duration of dryness. This duration will be obtained from end date of dryness and start date of dryness for longest interval. If subjects obtain dryness at end of study then duration will be obtained from end of treatment.

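### SAP Addendum 2.6.1.2.5 computes 'maximum duration of dryness' as time from first treatment to onset of dryness, contradicting the longest-dry-interval definition in 2.1.1; the time-to-dryness output in 2.6.1.2.4 has a wrong probability label and an inconsistent event

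*SAP*

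**What the plan says.** **Definition (SAP Addendum 1.0, Section 2.1.1).** Maximum duration of dry retina is the longest consecutive interval of dryness: "This duration will be obtained from end date of dryness and start date of dryness for longest interval". A further sentence covers the end of the study: "If subjects obtain dryness at end of study then duration will be obtained from end of treatment". The same section says that "study treatment end date is defined as the last date of study treatment is administered", and Protocol Section 3 says "For all patients, the last potential study treatment will be at the Week 40 visit or at the Week 44 visit". Dry retina is defined there as absence of IRF, SRF and sub-RPE fluid.

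**Maximum duration of dryness (2.6.1.2.5).** The clock starts at the start of treatment, the event is dryness, and the event's end date is the start of dryness. Censoring is for "Absence of dryness until EOS" or for early discontinuation while not dry. Duration is end minus start plus 1, with the note "Maximum duration will be used". The Kaplan-Meier (KM) display lists "total number of patients having fluids (risk), number of patients under achieved maximum duration (event), probability of maximum duration of dryness (survival probability".

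**Time to dryness (2.6.1.2.4).** The clock runs from the IVT injection to the first dry retina. The risk set is eyes without a dry retina, and the survival estimate is labelled as the probability of a dry retina. The event row mentions only IRF and SRF, joined by and/or.

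**Change log, Addendum V1.0.** The entry for 2.1.1 adds the definition of maximum duration. The entry for 2.6.1.2.5 reads "Logic for start date, end date and censor was updated".

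**The concern.** A duration of dryness needs a date on which dryness ends, and the 2.6.1.2.5 table has none. Its start, end, risk set and censoring rules all describe waiting for dryness to begin. For an eye with one dry spell it repeats 2.6.1.2.4, and no KM table in the Addendum then measures how long eyes stay dry.

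The section promises a median, a 95% CI and a plot under the title of maximum duration. If the table is followed, an eye that dries early and stays dry contributes a small value and an eye that dries late a large one. A reader would take a long median as good news when it means slow drying.

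Two smaller problems sit beside this one in 2.6.1.2.4: a label that names the complement of what is estimated, and an event that does not match the general definition.

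**Working it through.** **1. The two rules side by side**

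| Element | 2.1.1 | 2.6.1.2.5 table |
|---|---|---|
| Start | start of the longest dry interval | start of treatment |
| End | end of that interval | start of dryness |
| At risk | (implied) eyes still dry | eyes having fluid |
| Never-dry eye | no dry interval | censored at EOS or discontinuation |

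**2. Worked values.** Inputs: scheduled days from SAP Addendum Table 2-1 (first treatment Day 1, Week 4 = 28, Week 12 = 84, Week 32 = 224, Week 40 = 280, Week 44 = 308, Week 48 = 336) and the SAP formula (end − start) + 1. The eyes are hypothetical; no rates are assumed.

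| Eye | 2.6.1.2.5 table | 2.1.1, interval run to Week 48 |
|---|---|---|
| Dry Week 4 to Week 48 | 28 − 1 + 1 = 28 | 336 − 28 + 1 = 309 |
| Dry only from Week 44 | 308 − 1 + 1 = 308 | 336 − 308 + 1 = 29 |
| Never dry | 336 − 1 + 1 = 336, censored | no dry interval |

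For an eye that becomes dry on day w and stays dry to Week 48, the table gives w and 2.1.1 gives 336 − w + 1. The two sum to 337 for every w, so the ranking of such eyes is exactly reversed. If visits are placed 7 × week days after first treatment instead, each value counted from first treatment rises by one day (29, 309, 337); the direction is the same.

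**3. Does the note on using the maximum repair it?** Take an eye dry at Weeks 4 to 8, with fluid at Weeks 12 to 24, then dry at Weeks 32 to 48. Under 2.1.1 the first spell is 84 − 28 + 1 = 57 days to the first fluid visit and the second is 336 − 224 + 1 = 113, so the maximum is 113. Under the table the candidates are 28 (first onset) and 224 (later onset). Taking the maximum selects 224, still counted from first treatment.

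**4. The end-of-study sentence in 2.1.1.** Treatment end means the last injection, at Week 40 or Week 44 at the latest. If that date closes the interval of an eye dry since Week 4, the duration is 280 − 28 + 1 = 253 or 308 − 28 + 1 = 281, instead of 309. The sentence can equally be read as giving a start date to an eye first dry at Week 48. The text does not say which.

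**5. The label in 2.6.1.2.4.** With event dry and risk set not dry, the KM estimate S(t) is the probability of not yet being dry. As an illustration with five assumed eyes (first dry at Weeks 4, 8, 12 and 20, and one never dry), S at Week 12 is 4/5 × 3/4 × 2/3 = 0.4, while 3/5 = 0.6 have become dry. The column would print 0.4 as the probability of a dry retina. The parallel table in 2.6.1.6.1 labels its S(t) correctly, as the probability of disease activity where the event is no disease activity. The label alone does not alter the median, its CI or the curve.

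**6. The event in 2.6.1.2.4.** Section 2.1.1 counts sub-RPE fluid; the event row does not. Read literally, and/or also allows two events: both fluids absent, or either one absent. Each choice can change the first visit that counts as dry, and so the median, CI and curve.

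**The case against.** - **The general definition may govern, or the programming specifications may hold the right rule.** SAP Section 1 assigns further detail to table shells and dataset specifications that are not available here. Nothing in the SAP ranks 2.1.1 above 2.6.1.2.5, so the contradiction stands. This objection does bar a stronger inference: a reader might conclude that the reported duration results are reversed, but the documents do not show which rule was run.
- **The table may look freshly and wholly rewritten.** A reader might infer this from the change log. The log names only start date, end date and censoring. The event and duration rows match those in SAP Amendment 2.0, so the table mixes new rows with carried-over ones. The contradiction is nevertheless current, because the new definition and the new date rows came in the same Addendum.
- **The reversal is not universal.** A reader might extend it to all eyes. It is exact only for eyes that dry once and stay dry to the same end week.
- **IRF/SRF-only dryness may be deliberate in 2.6.1.2.4.** Sections 2.6.1.2.2 and 2.6.1.2.3 report IRF/SRF states apart from sub-RPE fluid, so a local definition is possible. The documents do not settle this. The ambiguity of and/or stands either way.
- **The label carries the words survival probability in brackets.** That lowers the risk of misreading but does not make the label right.
- **These outputs carry little weight.** Protocol 12.5.1 names KM analyses only for time to first q8w need and time to no disease activity. This is a fair limit on importance, not a defence of the specification.

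**Conclusion.** The 2.6.1.2.5 table is wrong as written for the quantity in its title: followed literally, it gives a time to onset of dryness. On Table 2-1 days the gap is 28 against 309 for an eye dry from Week 4 to Week 48, and 308 against 29 for an eye dry only from Week 44. These figures assume visits on their scheduled days and a dry interval counted to Week 48. They illustrate direction and do not estimate the effect in the trial.

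In 2.6.1.2.4 there are two separate faults. The label names the complement of S(t), which is a presentation error only. The event row does not agree with 2.1.1, which can change the result.

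All of this concerns descriptive SD-OCT outputs added by the SAP. The primary endpoint and the sample size are unaffected. It should be fixed, mainly because of the first fault; the other two alone would be minor.

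**What to change.** 1. **2.6.1.2.5.** Start at the beginning of the longest consecutive dry interval and end at its close (first later visit with fluid), censoring at the last assessment if still dry. This agrees with 2.1.1 and with the start, end and censoring rows of SAP Amendment 2.0. Relabel the risk set as still dry and S(t) as the probability of remaining dry.
2. **Never-dry eyes.** State one rule: either duration 0 within the FAS, or a KM limited to ever-dry eyes with the never-dry count and percentage reported. The documents do not settle this, and the second option departs from the statement that the analysis is on the FAS. Note that picking the longest spell and censoring open spells limits interpretation, since a shorter spell still open at the last assessment might have become the longest.
3. **2.1.1.** Replace the end-of-study sentence with the same censoring rule.
4. **2.6.1.2.4.** Report 1 − S(t), with complemented CI limits, as the cumulative probability of becoming dry, or relabel S(t) as the probability of not yet being dry.
5. **Dry retina.** Reconcile the definition across 2.1.1 and 2.6.1.2.3 to 2.6.1.2.5, replace and/or, and name any IRF/SRF-only version separately.

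The sponsor should also confirm which rule was programmed. The cost is SAP wording in those sections and re-derivation of two KM outputs; no new data are needed.

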2.6.1.3 Fluorescein angiography (FA)

The number and percentage of CNV location (subfocal, juxtafoveal, extrafoveal) at Week 12 will be presented for both study eye and fellow eye.

The summary statistics (n, mean, std, median, min and max) of area of lesion associated with CNV (mm**2) will be presented at Week 12 for study eye and fellow eye, along with change from Baseline and percentage change from Baseline.

The above analysis will be done only on the study eye. The analysis will be performed on the FAS.

2.6.1.4 Best corrected visual acuity (BCVA)

The summary statistics (n, mean, std, median, min and max) of BCVA for nAMD patients will be presented along with change and percentage change from Baseline in BCVA by visit. Along with below BCVA category.

- 1. BCVA (≤ 55 , 56 70 and ≥ 71).
- 2. Increase of ≥ 5 , ≥ 10 and ≥ 15 letters in BCVA from Baseline up to Week 48.
- 3. Loss of ≥ 5 , ≥ 10 , ≥ 15 and ≥ 30 letters in BCVA from Baseline up to Week 48.
- 4. BCVA \geq 84.

The above analysis will be done only on the study eye. The analysis will be performed on FAS.

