### **12.4.2 Statistical model, hypothesis, and method of analysis**

Descriptive statistics for the primary endpoint (actual value, change from Baseline, percentage change from Baseline) will be presented based on observed data using the FAS. Furthermore a two-sided 95% CI using Student's t-distribution will also be provided.

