### 12.5 Analysis of secondary endpoints

#### 12.5.1 Efficacy endpoints

All secondary efficacy analyses will be based on the FAS. The analyses performed at eye level will focus on the study eye only.

The secondary efficacy endpoints are as follows:

- Functional outcomes of brolocizumab
  - Change in BCVA from Baseline up to Week 48.
- Anatomical outcomes of brolocizumab
  - Percentage change in CNV lesion area measured by OCT-A from Baseline to Week 48.
  - Change in OCT-A features assessed by qualitative and quantitative criteria from Baseline by visit at Week 12 up to Week 48.
  - Change in SD-OCT features assessed by qualitative and quantitative criteria (e.g. CSFT, sub- and/or intraretinal fluid, sub-RPE fluid) from Baseline by visit at Week 12 up to Week 48.

The continuous functional and anatomical outcomes will be analyzed using the same primary method of analysis as the primary efficacy analysis. The factors in the respective model will be defined by the study Steering Committee. These details will be provided in the SAP. The qualitative dichotomous anatomical outcomes with 2 categories will be assessed using Cochran's Q Test and those with more than 2 categories by the Generalized McNemar's Test. In addition, the functional and anatomical outcomes will be described descriptively.

- Dosing regimen of brolocizumab
  - Proportion of patients who are maintained on an exclusive q12w interval following the loading phase through Week 48.
  - The probability of the first q12w interval for determining successful q12w maintenance at Week 48.
  - Time from last IVT injection in the initiation phase to first visit with no disease activity

The binomial proportion and 95% confidence interval (CI) using the Clopper-Pearson method will be provided for disease status (i.e. q12w treatment status) at each disease activity assessment visit. The estimate of the probability for a patient to be maintained on the q12w regimen up to end of treatment will be summarized based on a Kaplan-Meier analysis of time to first q8w need. The time from last IVT injection in the initiation phase to first visit with no disease activity will also be summarized using a Kaplan-Meier analysis. In addition, descriptive statistics will also be provided.

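### The SAP omits the 95% t interval that protocol 12.5.1 calls for on change in BCVA, CSFT and (indirectly) FA lesion area, and the matched analyses of qualitative outcomes

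*SAP*

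**What the plan says.** **Protocol.** Section 12.5.1 states: "The continuous functional and anatomical outcomes will be analyzed using the same primary method of analysis as the primary efficacy analysis". The primary method in 12.4.2 is descriptive statistics on observed data in the FAS, and then: "Furthermore a two-sided 95% CI using Student's t-distribution will also be provided". For qualitative outcomes 12.5.1 continues: "The qualitative dichotomous anatomical outcomes with 2 categories will be assessed using Cochran's Q Test". It gives the generalized McNemar test to outcomes with more than two categories. Descriptive summaries are to be provided on top of these methods, not in their place.

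**SAP Addendum.**
- BCVA (2.6.1.4): "The summary statistics (n, mean, std, median, min and max) of BCVA for nAMD patients will be presented along with change", plus percentage change and letter categories. No interval is named.
- CSFT (2.6.1.2.1): "Summary statistics of central sub-field retinal thickness (CSFT) measured by SD-OCT for" the study patients, by visit, with change and percentage change. No interval is named.
- FA lesion area (2.6.1.3): the same set of summary statistics at Week 12, with change. No interval is named.
- Fluid and PED nature (2.6.1.2.2): "The number and percentage of patients with below fluid will presented by visit". Change from Baseline is not mentioned.
- Dry retina (2.6.1.2.3 to 2.6.1.2.5): Clopper-Pearson 95% CIs by visit for the proportions without IRF and SRF, without IRF, without SRF and without sub-RPE fluid. Kaplan-Meier medians with 95% CIs follow for time to dryness and maximum duration of dryness.
- OCT-A lesion area to Week 48 (2.6.1.1): the t interval is kept.

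**The concern.** The study is single-arm, tests no hypothesis, and is sized entirely on the half-width of a confidence interval (protocol 12.8.1). The interval is therefore its inference. BCVA change is the only functional outcome in the protocol's secondary efficacy list, and CSFT is the first example named in the SD-OCT endpoint ("Change in SD-OCT features assessed by qualitative and quantitative criteria (e.g. CSFT, sub- and/or intraretinal fluid, sub-RPE fluid) from Baseline by visit at Week 12"). If the SAP is followed literally, these mean changes are reported without the interval that the protocol attaches to them.

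The matched tests raise a related issue. The fluid endpoint is a change from Baseline in the same eyes, and separate percentages at each visit do not determine how precisely that change is estimated.

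**Working it through.** **1. The plan's own precision figure.** Inputs from protocol 12.8.1: SD 35, target half-width 5.0, 10% loss. Normal approximation: (1.96 × 35 / 5)² = 188.2, so 189. With Student's t, n = 189 gives a half-width of 5.02, which rounds to 5.0. 189 / 0.90 = 210. Both stated figures reproduce. They concern the primary endpoint only; the documents give no SD or target precision for a secondary endpoint.

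**2. Protocol against SAP.**

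| Outcome | Protocol 12.5.1 | SAP Addendum |
|---|---|---|
| OCT-A area, Week 48 | t interval | t interval |
| BCVA change | t interval | none stated |
| CSFT change | t interval | none stated |
| FA area change | t interval, through the general wording and Table 2-1 | none stated |
| Fluid, two categories | Cochran's Q | by-visit percentages, Clopper-Pearson, Kaplan-Meier for dryness |
| PED nature, more than two categories | generalized McNemar | by-visit percentages |

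Where the SAP wants an interval it says so (2.5.1, 2.6.1.1, 2.6.1.2.3 to 2.6.1.2.5, 2.6.1.5). Silence in 2.6.1.2.1, 2.6.1.3 and 2.6.1.4 therefore reads as omission. SAP 5.4 has a generic means procedure with confidence limits that is tied to no endpoint. Its frequency code requests only a chi-square, and it has no code for either matched test.

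**3. Size of the missing t intervals.** Half-width = t(0.975, n − 1) × SD / √n. The multiplier of the SD is 0.161 at n = 150, 0.1435 at n = 189 and 0.136 at n = 210. All SDs below are assumptions.
- BCVA change: SD 10 with n = 190 gives 1.43 letters; SD 15 with n = 150 gives 2.42 letters.
- CSFT change, n = 189: SD 80 to 150 µm gives 11.5 to 21.5 µm.
- FA area change, n = 189: SD 1 to 3 mm² gives 0.14 to 0.43 mm².

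**4. Fluid.** For any IRF/SRF, inclusion criterion 4 requires that fluid at Baseline, and SAP Table 5-1 (INCL04) removes violators from the FAS. The Baseline proportion is therefore close to 100%, and the by-visit dry proportion is nearly the change itself. That proportion has an interval: at n = 189 and about 70% dry (assumed), Clopper-Pearson gives 62.8% to 76.3%.

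For a single fluid type the Baseline proportion is not fixed. Let b be the proportion of eyes that lose the fluid and c the proportion that gain it. The standard error of the paired change is √[(b + c − (b − c)²)/n]. Assume a fall from 60% to 35% with n = 189, so b − c = 0.25:
- correlation 0: b + c = 0.530, half-width 9.7 points
- correlation 0.3: b + c = 0.390, half-width 8.2 points
- correlation 0.5: b + c = 0.296, half-width 6.9 points

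The by-visit percentages are the same in all three cases, so they cannot show which applies.

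**5. Visits that every regimen shares.** The protocol plans no visits between injection visits after Week 16. A patient who stays on q12w is not seen at Weeks 24, 28, 36 and 40. A switch at Week 16 skips Weeks 20, 28, 36 and 44; at Week 20, it skips 24, 32 and 40; at Week 32, it skips 24, 28, 36 and 44. The common visits are Baseline and Weeks 4, 8, 12, 16 and 48.

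**The case against.** The strongest defence is that little is lost. BCVA and FA area report n, mean and SD, and CSFT does so under the general rule in SAP 2.1. If these are tabulated for the change itself, anyone can rebuild the t interval, and no decision rests on it. That is fair as to consequence. It does not bring the SAP into line with the protocol, and it shows how small the repair is.

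Three stronger readings are tempting, and the documents do not support them.
- *A reader might infer that the fluid objectives have no stated precision.* They keep Clopper-Pearson intervals by visit and Kaplan-Meier intervals for dryness. For any IRF/SRF the paired change is nearly recovered, apart from eyes where the reading centre disagrees with the investigator's Baseline finding. The gap is confined to IRF alone, SRF alone, sub-RPE fluid and PED nature.
- *A reader might infer that Cochran's Q cannot be computed because no patient attends all 13 analysis visits in SAP Table 2-1.* The protocol names no set of visits for the test. The attendance pattern is a reason to state the set, not evidence that the test was impossible.
- *A reader might infer that the departure is unexplained.* SAP Section 4, on changes to protocol-specified analyses, shows only its heading in the available copy, and the change log records an addition there concerning the estimand. An explanation cannot be ruled out.

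FA is also a weaker case than BCVA or CSFT. It stands in protocol Table 2-1 but not in the list in 12.5.1, and is reached only through the general phrase on anatomical outcomes.

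**Conclusion.** The point holds in a limited form. The SAP Addendum leaves out the two-sided 95% t interval for change in BCVA and CSFT, and less directly FA lesion area. It also leaves out both matched tests that protocol 12.5.1 assigns to qualitative anatomical outcomes. This departs from a specified analysis in a study whose sample size rests on interval width, so it should be corrected. It does not touch the primary endpoint or the Week 48 OCT-A endpoint.

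Under the assumed SDs the absent BCVA half-width is about 1.4 to 2.4 letters. For one fluid type under the assumed 60% to 35% fall, the paired half-width is 6.9 to 9.7 points depending on within-patient correlation. These sizes are illustrative; the finding itself rests on comparing the two texts.

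**What to change.** - **SAP 2.6.1.2.1 and 2.6.1.4:** add the two-sided 95% t interval for mean change from Baseline, at least at Weeks 12 and 48.
- **SAP 2.6.1.3:** add the same interval at Week 12.
- **SAP 2.6.1.2.2:** add the paired change in proportion from Baseline, with 95% CI, for IRF, SRF and sub-RPE fluid at Weeks 12 and 48. For PED nature, add a generalized McNemar (Stuart-Maxwell) analysis. The SAP records PED nature only when sub-RPE fluid or PED is present, so a level for PED absent is needed to give every eye a category at both visits.
- **If the sponsor prefers to drop the matched tests:** record and justify that in SAP Section 4.
- **If Cochran's Q is kept:** limit it to Baseline and Weeks 4, 8, 12, 16 and 48.

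The t intervals cost a sentence and a column in existing tables. The paired fluid and PED analyses need a little more programming, including the extra PED level. No new data are collected.
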